#### 1- Introduction/Background/Purpose:

In the United States, preterm premature rupture of membranes (PPROM) complicates 4% of pregnancies annually. This pregnancy complication is a major contributor to preterm births and results in neonatal morbidity and mortality. Without treatment, 70-80% of women deliver within the 1st week following membrane rupture. Multiple trials have proven that antibiotics given to this population prolong the latency from time of PPROM to delivery, hence reducing maternal and neonatal morbidities.

According to the American College of Obstetrics and Gynecology, the current standard of care for PPROM subjects between the gestational age of 24 weeks and 0 days and 33 weeks and 6 days, is to administer ampicillin 2 gm IV every 6 hours for 48 hours followed by amoxicillin 250 mg orally every 8 hours for 5 days, with erythromycin 250 mg IV every 6 hours for 48 hours followed by 500 mg orally every 8 hours for 5 days. In this regimen, multiple doses of intravenous (IV) and oral (PO) doses of erythromycin are needed to achieve the desired outcome. Erythromycin can cause GI upset and some subjects do not tolerate this regimen over the course of 7 days. In addition, there is a national shortage of erythromycin, and published expert opinion proposed to use a second-generation macrolide (azithromycin) instead of erythromycin. This strategy was adopted nationwide including our maternal center at UTMB since 2014. Compared to erythromycin, advantages of azithromycin include:

- It is taken once orally (due to its long intracellular half-life).
- The entire regimen is much cheaper than the multiple does of erythromycin (23 doses).
- It has less gastrointestinal adverse effects.

As a result, azithromycin is now commonly being used as a substitute for erythromycin on many labor and delivery units around the country.

Despite its common use, there exists no level 1 evidence that azithromycin is equivalent to erythromycin. Haas and colleagues published a retrospective comparison of the two regimens in 2014 and concluded that the substitution of azithromycin for erythromycin in the recommended antibiotic regimen did not impact latency or any other measured maternal or fetal outcomes. This study, however, was limited by its non-randomized retrospective nature. Our objective is to compare the effectiveness of the 2 regimens in prolonging pregnancy after PPROM.

#### 2- Concise summary of project:

This trial will be a comparative effectiveness pragmatic multi-site randomized trial performed in singleton pregnancies with the diagnosis of PPROM between 24 weeks and 0 days - 32 weeks and 6 days. It will be comparing two well-accepted standardized treatments of care in this subject population: Erythromycin (FDA Category B) versus Azithromycin (FDA Category B). Our primary outcome will be the proportion of women still pregnant by day 7 after the diagnosis of PPROM is made. Our working hypothesis is that there is no measurable difference in the primary outcome between the group randomized to the azithromycin regimen versus the group randomized to the erythromycin regimen. Our secondary outcome will be latency defined as interval from PPROM to delivery. We propose a total of 324 subjects will be needed to complete the study.

# United States, Texas

St. David's North Austin Medical Center Recruiting Austin, Texas, United States, 78758 Contact: [name] [contact] [contact] PI : [name] [contact]

Each center had the protocol reviewed and approved independently by their local IRB before participating in this trial or recruiting.

UTMB is the leading site for this trial. There is no specific accrual number per site. Across multi-sites, randomization is centralized. UTMB perinatal research division coordinates randomization assignment schedule by increments of blocks of 10 as enrollment is ongoing. Each block has 10 subjects randomized to either intervention A or B which is independent and does not affect the remaining sequence. For example, Block #1 has the first 10 subjects, within the block we will have 5 in intervention A and 5 in intervention B randomization independent of the remaining sequence or Block. Each site will be given 1-3 blocks of 10 increments for randomization. This approach is independent of the remaining sequence or blocks, thus not affecting the remaining randomization sequence.

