#### 3.1 Screening, Recruitment and Consenting:

Under the direction of the PI, trained research staff will be available 24/7 to screen and consent subjects according to study protocol. Medical records of all potential subjects with a diagnosis of PPROM will be reviewed and those who satisfy inclusion and exclusion criteria will be approached and a written informed consent will be obtained. A screening log will be used to track all subjects approached for the study. Potential subjects may be patients of the investigators.

Subjects will be enrolled at the time of admission to labor and delivery (L&D) or thereafter. Subjects will be recruited, enrolled and consented in a private room in labor and delivery or antepartum units in order to respect the privacy of potential subjects. Subjects will be given all the time needed in order to fully understand and read the consent forms. All questions will be fully answered. If needed, a certified language interpreter will be available and Spanish consents will be used as appropriate. Women will only be randomized on our labor and delivery or antepartum units when the decision to initiate antibiotics is made, AND they continue to be eligible (using a randomization screen).

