#### 3.2 Randomization

A confidential computer-generated simple randomization scheme (using STATA 14, Dallas, Tx) will be prepared and provided on an ongoing basis to our study coordinator. A randomization log with group assignment, subject name and medical record number will be used to track the randomization process. Across multi-sites, randomization is centralized. UTMB perinatal research division synchronizes randomization assignment schedule by increments of blocks of 10 as enrollment is ongoing.

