#### 3.3. Antibiotics Disposal and Administration

Once a subject is consented and randomized, the appropriate antibiotics according to group assignment will be dispensed by the regular hospital pharmacists after order is placed in EPIC (as part of standard procedure at UTMB). Both drugs are standard of care at UTMB. This is a pragmatic/comparative effectiveness of two standard of care therapies. Regular hospital pharmacy currently stores and disposes the drugs and subject's insurance will be responsible for paying for either antibiotic, as any other subject not in the study. Floor nurses will be administering antibiotics. Research staff will be checking medication administration record (MAR) in EPiC for compliance to the research protocol; if an antibiotic is withheld for any reason the staff will inform the PI and report it as a protocol deviation which may potentially affect the integrity of the data for that subject.

The subject will be included in the analysis by intent-to-treat once the assigned antibiotics are dispensed from inpatient pharmacy and sequential number posted on the subject specific randomization form.

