#### **3.4.** Baseline Procedures

Routine PPROM care will be provided by the subjects' clinical providers.

Trained and experienced research staff will be responsible for all research data abstraction.

The PI will review and validate the diagnosis for all subjects identified to have the primary outcomes. These reviews will be conducted masked to treatment group. If there is uncertainty, a will review the chart, discuss with the co-investigators as needed and make a final determination regarding the outcome.

Maternal and neonatal outcomes will be assessed in the hospital following the delivery (on an ongoing basis until discharge).

Several data collection forms will be used during these processes. Data on these forms, devoid of personal identifiers, will be securely stored at our perinatal research division.

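### Fixed, published 5:5 blocks of 10 issued by site could reveal up to 1 in 6 assignments to staff who see earlier ones; *simple* is the wrong label, and the analysis does not use site

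*Combined protocol and SAP*

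**What the plan says.** Section 3.2 describes "A confidential computer-generated simple randomization scheme", which "will be prepared and provided on an ongoing basis to our study coordinator". The same paragraph says the schedule is issued in blocks of 10.

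The site section (heading United States, Texas) gives the structure: "within the block we will have 5 in intervention A and 5 in intervention B". It then says "Each site will be given 1-3 blocks of 10 increments for randomization". No other block size appears. It also says that randomization is centralized and that no accrual number is set per site.

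On who can see what:

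- Section 3.2 provides for a randomization log that holds group assignment alongside subject identifiers.
- Section 3.3 says: "Research staff will be checking medication administration record (MAR) in EPiC for compliance to the research protocol".
- The only masking described is of the primary-outcome review in section 3.4: "These reviews will be conducted masked to treatment group".
- The regimens in section 4 look different: one oral macrolide dose in one arm, repeated IV then oral doses in the other.

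Safeguards are also stated. Section 3.1 has eligibility confirmed again at randomization, and "A screening log will be used to track all subjects approached for the study". Section 3.3 refers to a "sequential number posted on the subject specific randomization form".

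Section 13 tests the primary outcome with a univariable method and adds a multivariable logistic model without listing its covariates. Site appears in neither.

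**The concern.** Simple randomization has no balance constraint, so a scheme that forces five and five in every ten is not simple. It is permuted blocks, and because whole blocks go to sites it is in effect stratified by site.

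The structure matters because treatment is not described as masked. Once one arm has used its five places, the rest of the block is known. The printed size tells any reader of the protocol where that happens. Calling the list confidential and central protects the list, but does not prevent deduction from assignments already seen.

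At stake is selection at enrolment. Where the next arm is certain, the decision to approach a woman, or when to seek consent, could depend on it. Intent-to-treat analysis does not repair that. A screening log helps only in part, because it records those who were approached.

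The second, smaller matter is that the analysis does not reflect the site blocks by which assignments are balanced.

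**Working it through.** **The plan's own figure.** Inputs from section 13: 70% undelivered in both arms, margin 0.15, one-sided alpha 0.025, power 80%.

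n per arm = (1.960 + 0.842)² × 2 × 0.7 × 0.3 / 0.15² = 7.849 × 0.42 / 0.0225 = 146.5, so 147. Total 294; 294 × 1.10 = 323.4, so 324. This reproduces the plan and does not depend on the present point. The plan gives no figure for predictability.

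**Certain assignments in a completed block.** With block size 2m and m per arm, the expected number is 2m/(m + 1). For m = 5 this is 10/6 = 1.667, or 16.7%. Enumerating all 252 possible 5:5 sequences agrees:

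| Place in block | 1-5 | 6 | 7 | 8 | 9 | 10 |
|---|---|---|---|---|---|---|
| Probability that it is certain | 0 | 0.8% | 4.8% | 16.7% | 44.4% | 100% |

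**Upper bound for the trial.** 324/6 = 54, or 294/6 = 49 on the uninflated size. This needs every block completed and an observer who has seen every earlier assignment in the block and knows where it began.

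**Unfinished blocks.** The first five places are never certain, so stopping mid-block lowers the share. A site stopping at 25 has two full blocks: 2 × 1.667 / 25 = 13.3%. If k sites each stop five into a block, the expected number is (324 − 5k)/6. The number of sites is an assumption.

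| k | Certain | Share of 324 |
|---|---|---|
| 5 | 49.8 | 15.4% |
| 10 | 45.7 | 14.1% |
| 20 | 37.3 | 11.5% |

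**Best guess.** Always guessing the arm with more places left is right in (m + 2^(2m−1)/C(2m,m) − ½)/2m = (5 + 512/252 − 0.5)/10 = 65.3% of assignments in completed blocks, against 50% under truly simple randomization.

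**Varying sizes.** These were simulated for an observer who knows the set of sizes but not the size of each block, at sites of 20, 30 and 60 subjects (4,000 runs each):

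| Block sizes | Certain | Best guess |
|---|---|---|
| Fixed 10 | 16.7-16.8% | 65.3% |
| 8/10/12 | 1.76, 1.65, 1.31% | 64.0, 64.2, 64.8% |
| 10/12/14/16 | 0.90, 0.86, 0.74% | 61.6, 62.6, 63.2% |
| 4/6/8 | 2.5, 2.3, 2.4% | 67.0, 67.5, 67.8% |

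Sites of 20, 30 and 60 all end on a completed fixed block, which flatters the change. At 25 subjects, fixed 10 gives 13.3% certain and a 63.5% best guess; 8/10/12 gives 1.9% and 63.9%. At 15 and 35 subjects the best guess is likewise slightly higher under 8/10/12 (62.6 v 62.2%; 64.3 v 64.0%). So 8/10/12 removes most certainty, but does not reduce guessing at such sites.

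**Site in the analysis.** The between-site SD is not in the documents; 5 to 10 points is assumed. The share of outcome variance due to site is f = 0.05²/0.21 = 1.2% to 0.10²/0.21 = 4.8%. Ignoring it makes the actual one-sided alpha 1 − Φ(1.96/√(1 − f)) = 0.0243 to 0.0223, below the nominal 0.025. A simulation with 30 blocks over 5 or 8 unequal sites (150 per arm, 200,000 trials per cell) compared an unstratified interval with a Mantel-Haenszel one:

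| Between-site SD | Power, unstratified | Power, stratified |
|---|---|---|
| 0 | 81.1-81.2% | 80.9-81.0% |
| 5 points | 81.4-81.5% | 81.6-81.7% |
| 10 points | 82.0-82.1% | 82.9% |

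**The case against.** The strongest reply is that the exposure depends on facts the plan does not state. Randomization is central and confidential, the list goes to a coordinator, and the text does not say that those who seek consent also see earlier assignments. Parts of the document were not available and may describe a concealment step. This stands: if recruiters cannot see earlier assignments, the predictability figures do not apply.

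The scope for selection is also narrow. Section 3.1 has all PPROM records reviewed and eligible women approached, and randomizes only once the decision to start antibiotics is made. Both arms are described as standard of care, and section 2 expects no difference. These points lower the likelihood of selection; they do not change what an observer could deduce.

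A reader might infer that 54 assignments will be known in advance. The documents do not support that. It is a ceiling, and with no accrual number per site, unfinished blocks are to be expected. A reader might also infer that concealment failed or that the comparison is biased; nothing in the documents shows either.

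The allotment of one to three blocks is ambiguous: it may be a site's total or the quantity per issue. If it is a total, 324/30 = 10.8, so at least 11 sites of at most 30 are needed, and neither the 60-subject case nor the 5- and 8-site simulation describes the trial.

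On site, one might infer that leaving it out inflates the false-positive rate. It does the opposite: the unstratified test is slightly conservative. The logistic model could include site, although the plan does not say so. Finally, the label *simple* misleads little, since the same paragraph mentions blocks of 10.

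**Conclusion.** The point holds as a minor design weakness. The scheme is fixed permuted blocks of 10 issued by site, with a published size and no described masking of treatment. For an observer with full sight of a site's earlier assignments, up to 1 in 6 are certain; with unfinished blocks a more realistic range is about 11-15%, given an assumed 5 to 20 sites stopping mid-block. No bias, alpha inflation or power loss from selection is claimed, because the documents give no figure from which to derive one.

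Omitting site is conservative. At an assumed between-site SD of 5 to 10 points, stratifying gains about 0.1 to 0.9 power points in simulation; if sites do not differ, it costs about 0.1 point. The reason to do it is to match the analysis to the way assignments are balanced, rather than to rescue power.

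**What to change.** 1. **Analysis.** In section 13, state that the primary outcome will be analysed with a site-stratified (Mantel-Haenszel) risk difference and its 95% CI, judged against the 15-point margin. Cost: one sentence and no new data.

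2. **Blocks not yet issued.** Use randomly varying sizes that are not disclosed to sites or printed in the site protocol. Sizes of 10-16 are preferable (about 1% certain, best guess about 62-63%). The set 8/10/12 also cuts certainty, to about 2%, but does not reduce guessing at sites that stop mid-block. Small sets such as 4/6/8 raise the best-guess rate to about 67-68%. Varying sizes remove most certainty, not guessing. Cost: an amendment at each site's IRB, since each centre approved the protocol independently; a mixed scheme, since a site is listed as recruiting; and a largest within-site imbalance of 8 instead of 5.

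3. **Wording only.** In section 3.2, replace *simple* with *permuted blocks issued by site*. The same edit could say whether those who seek consent can see earlier assignments, since that decides whether the predictability figures apply.

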# 4- Study procedures:

Eligible subjects will be approached, and those who consent will be randomized to one of the two groups below in a 1-to-1 allocation.

- Erythromycin group: Ampicillin 2 gm IV every 6 hours first 2 days followed by amoxicillin 250 mg PO every 8 hours for next 5 days with erythromycin 250 mg IV every 6 hours for first 2 days followed by 500 mg PO every 8 hours for next 5 days (standard of care at UTMB).
- Azithromycin group: Ampicillin 2 gm IV every 6 hours first 2 days followed by amoxicillin 500 mg PO every 8 hours for next 5 days with azithromycin 1 gm PO once at randomization (Standard of care at UTMB).
   Both groups receive a total of 7 days of antibiotics as per standard of care at

The remaining standard of care will be the same for both groups concerning the management of PPROM according to NICHD/ACOG guidelines including GBS prophylaxis.

GBS chemoprophylaxis is beyond the scope of this trial, since we are randomizing the portion of macrolides only and not the Ampicillin portion that actually covers GBS. As noted, this regimen of intravenous ampicillin/ amoxicillin, is standard on both interventions and covers GBS. GBS cultures and GBS treatment is left per providers' discretion beyond our intervention period (7 days of latency antibiotics). In addition, drug adverse effects profiles between the two will be assessed in a post treatment subject survey. Subjects will complete a survey before being discharged from the hospital after receiving the assigned antibiotic regimen. Any questions will be answered and sufficient time will be given for the subject to fill the survey. Data will be collected retrospectively from EPIC EMR:

- Time of initiation of antibiotics to delivery.
- Maternal outcomes: chorioamnionitis, postpartum infectious morbidity, placental abruption
- Route of delivery

UTMB.

- Gestational age at delivery
- Adverse events: Allergic reactions (anaphylaxis, angioedema, skin rashes including Stevens Johnson and Toxic Epidermal necrolysis), GI symptoms (vomiting, diarrhea, constipation, ileus)
- Neonatal outcomes: perinatal death, need for oxygen supplementation (not intubated), ventilation support (intubated), necrotizing enterocolitis (NEC) stage 2 or 3, duration of ventilator support (intubated), NICU days and neonatal infection/sepsis, individually and as a composite.

Both survey forms and data forms are attached with protocol application.

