# 12-Potential benefits:

In the background of erythromycin nationwide shortage, this will be the first level 1 trial to show that azithromycin may be equivalent to erythromycin in delaying delivery in patients with PPROM. This study may show for the first time that current alternative practice with azithromycin is as effective as erythromycin but with less adverse effects, less costly and easy administration.

13-**Statistical approach:** Analysis will be performed by intent to treat. Univariable analysis (such as t-test, Mann-Whitney or Chi-square) will be used for descriptive statistics such as patient demographics and assessment of primary outcome. Multivariable logistic analysis will be used to account for potential confounding variables. Sample size was calculated using a noninferiority trial design. Azithromycin will be tested against erythromycin for PPROM. The primary outcome will be the proportion of subjects undelivered

by day 7. For the sample size calculation, it is assumed the proportion undelivered in the erythromycin group would be 70% (pi = 0.7) based on Haas et al study. We considered that a difference in undelivered rate as large as 15% in favor of erythromycin would allow azithromycin to be non-inferior (delta = 0.15). This study will use 80% power to confirm non-inferiority and a one-sided confidence level of 97.5%.

Estimated sample size for two-sample comparison of proportions (non-inferiority)

Null hypothesis: p2 - p1 � delta (inferior), where:

pi (entered in command) is the overall proportion of participants expected to experience the outcome if the treatments are non-inferior, and delta is the smallest change in proportions between groups (p2 - p1) which would still be clinically important.

Alternative hypothesis: p2 - p1 < delta (non-inferior)

Note: a non-inferiority analysis is one-sided.

```
Assumptions:

power = 0.8000

alpha = 0.0250 (one-sided)

pi = 0.7000

delta = 0.1500

estimated required sample size (per group) = 147
```

The total estimated sample size is 294. Assuming 10% loss to follow, this study proposes a total of 324 subjects will be needed to complete the study. The STAT 14 (Dallas, Tx) will be used for statistical computations. This trial will be registered with Clinical Trials Register (Clinicaltrials.gov), before recruitment is initiated and after IRB approval."

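### The arms are written with different oral amoxicillin doses (250 mg and 500 mg every 8 hours), although the protocol says only the macrolide is randomised

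*Combined protocol and SAP*

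**What the plan says.** Section 4 defines the arms in adjacent bullets. Both start with ampicillin 2 g intravenously every 6 hours for two days. In the erythromycin arm this is "followed by amoxicillin 250 mg PO every 8 hours for next 5 days with erythromycin 250 mg IV every 6 hours". In the azithromycin arm it is "followed by amoxicillin 500 mg PO every 8 hours for next 5 days with azithromycin 1 gm PO once at randomization". Each regimen is labelled standard of care at the lead centre.

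The same section states what is randomised: "we are randomizing the portion of macrolides only and not the Ampicillin portion that actually covers GBS". It adds that "this regimen of intravenous ampicillin/ amoxicillin, is standard on both interventions and covers GBS". Section 1 (Introduction/Background/Purpose) describes the recommended regimen as including "amoxicillin 250 mg orally every 8 hours for 5 days". No supplied text explains the 500 mg.

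The question being asked is framed in two ways. Section 1 says "Our objective is to compare the effectiveness of the 2 regimens in prolonging pregnancy after PPROM", which compares regimens. Section 13 (Statistical approach) says "Azithromycin will be tested against erythromycin for PPROM", which compares drugs. Section 12 (Potential benefits) hopes to show that practice with "azithromycin is as effective as erythromycin but with less adverse effects, less costly and easy administration".

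**The concern.** Two things differ between the arms as written: the macrolide and the oral amoxicillin dose. Randomisation still gives a valid comparison of the two packages. It does not give a comparison of azithromycin with erythromycin, because every woman assigned azithromycin is also assigned twice the amoxicillin dose.

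Two comparisons are affected. The first is the primary outcome, the proportion undelivered at day 7 from diagnosis, since the oral phase falls before that point. The second is gastrointestinal tolerability, which is collected by patient survey and is one of the advantages expected for azithromycin. The multivariable logistic model in section 13 cannot help, because dose and arm would be the same variable.

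The matter is sharper in a non-inferiority trial. Any benefit given only to the test arm pushes towards the claim being tested.

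**Working it through.** **1. The written doses (section 4).**

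| | Erythromycin arm | Azithromycin arm |
|---|---|---|
| IV ampicillin | 2 g × 4/day × 2 days = 16 g | 16 g |
| Oral amoxicillin, doses | 3/day × 5 days = 15 | 15 |
| Oral amoxicillin, total | 15 × 250 mg = 3.75 g | 15 × 500 mg = 7.5 g |
| Beta-lactam by mass | 16 + 3.75 = 19.75 g | 16 + 7.5 = 23.5 g |

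The oral total is doubled. The whole-course ratio is 23.5 / 19.75 = 1.19, about 19% more. That sum mixes two drugs and two routes, so it is only indicative.

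**2. The plan's sample size (section 13).** The inputs are 70% undelivered, margin 0.15, one-sided alpha 0.025 and power 0.80.

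n per group = (1.96 + 0.842)² × 2 × 0.70 × 0.30 / 0.15² ≈ 146.5, so 147.

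The total is 294, and 294 × 1.10 = 323.4, so 324. The plan's figures are reproduced, and equalising the amoxicillin dose does not change them.

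**3. How many women would be exposed.** Women who deliver in the first two days never reach the phase where the doses differ. Those undelivered at day 7 would receive the full oral course, if antibiotics start at diagnosis and are completed.

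- At the assumed 70%, with 324 / 2 = 162 per arm: 0.70 × 162 = 113.4, about 113 women.
- If the azithromycin rate were at the margin, 0.70 − 0.15 = 0.55: 0.55 × 162 = 89.1, about 89 women.
- On the 147 per arm before the loss allowance: 0.70 × 147 = 102.9, about 103 women.

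Women delivering between the end of the IV phase and day 7 would be partly exposed and are not in these counts.

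**4. What a dose effect could do (illustration only).** The documents give no effect of amoxicillin dose on latency, so the effects below are assumptions. Take 147 per arm and 70% undelivered on erythromycin. Let b be the change in the azithromycin arm's day-7 rate caused by the higher dose.

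- *Dose helps, and the macrolide is truly worse by the full 15 points.* The azithromycin rate is p = 0.55 + b, with SE = √[(0.21 + p(1 − p)) / 147]. The chance of declaring non-inferiority is Φ(b / SE − 1.96).
- *Dose harms, and the macrolides are equally effective.* The azithromycin rate is p = 0.70 − b, with SE from the same formula. The power is Φ((0.15 − b) / SE − 1.96).

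| Assumed b | False non-inferiority if dose helps | Power if dose harms |
|---|---|---|
| 0 points | 2.5% | 80.1% |
| 2 points | 5.5% | 67.4% |
| 5 points | 14.5% | 44.9% |
| 10 points | 44.9% | 14.5% |

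The error can run either way, and with no dose effect there is no bias. No comparable calculation is possible for gastrointestinal symptoms.

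**The case against.** The strongest reply is that this is a pragmatic comparison of two regimens. Sections 1 and 2 use that language, and section 4 calls each whole regimen standard of care. For that question, differing components do no harm. This stands as far as it goes, but the statement that only macrolides are randomised would then be wrong. Section 13 names the drugs alone, and section 12 expects the trial to show that azithromycin may be equivalent to erythromycin. The section 12 sentence quoted above has current practice with azithromycin as its subject, so it carries less weight than the other two.

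A second reply is that the macrolides-only sentence concerns group B streptococcus cover and contrasts macrolides with ampicillin, which is identical in both arms. The setting is as described. It is still the protocol's explicit statement of what is randomised, and the companion sentence includes amoxicillin.

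Third, the 500 mg may be a copying error, since the erythromycin bullet has the same oral dose and schedule for erythromycin itself. The flow diagram and data forms are not available here. If the error never reached orders, there is no bias. But this is the operative dosing text: section 3.3 has staff check administration against the protocol, and each centre's IRB approved it. What any site actually ordered cannot be known from the documents.

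Fourth, a change in mid-trial is more than a typing correction. It would need review at each centre. If 500 mg has been given, dose would then vary within the arm by calendar time, which is not randomised. Both points stand and affect the cost and the reporting, but they do not justify leaving the text as it is.

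**Conclusion.** The concern holds. The written arms differ two-fold in oral amoxicillin (3.75 g against 7.5 g), without explanation and contrary to the protocol's own statement of what is randomised. If doses followed the text, the trial supports conclusions about whole regimens only, for both the day-7 outcome and gastrointestinal tolerability, and no analysis can recover the macrolide effect. About 113 of 162 women per arm would take the full oral course under the 70% assumption (about 89 on azithromycin at the margin), given that antibiotics start at diagnosis and are completed. The direction and size of any bias cannot be determined from the documents, nor can it be settled whether the difference is intended. It needs to be fixed because it lies in the definition of the intervention and limits what the trial can conclude.

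**What to change.** Decide which dose is meant, then do one of the following.

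- **If the difference is not intended:** write the same oral amoxicillin dose in both arms (250 mg every 8 hours matches section 1) and notify all sites.
- **If it is intended:** delete the macrolides-only wording, give the reason for 500 mg, and state the objective (section 1), the drug comparison (section 13), the expected benefit (section 12) and the conclusion as whole regimen against whole regimen.

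In either case, report by arm the amoxicillin dose actually given, from the medication administration record already checked under section 3.3. Analyse by dose only if doses varied within an arm, and treat that analysis as non-randomised. Otherwise, limit the conclusion for women already treated to whole regimens.

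The cost is a short amendment with review at each centre's IRB, a notice to sites, and one extra field from a record staff already check. Sample size and visits do not change.
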